Cover letter

Title: Comparison Between the Dentapen and Vibraject: a Randomized Clinical Study on the Administration of Local Anaesthesia in Adult Patients.

Date: January 14, 2025

STUDY PROTOCOL

Ethical Approval

The study was conducted in compliance with the Helsinki Declaration. Each participant in this study was given a thorough explanation of the procedures and signed a consent form attesting to their comprehension. Ethical approval was obtained from the research centre at Riyadh Elm University prior to conducting this research (FPGRP/2023/715/906/892). The informed consent was obtained from the participants who volunteered in this research.

Outcome Measurement

In this study, each patient received two injections in both sides of the maxilla buccally next to the first molar, with the type of injection being randomly assigned. Immediately following each local anaesthesia injection, patients were requested to rate their pain intensity using the Visual Analogue Scale. Additionally, heart rate measurements were taken before and after each injection to monitor physiological responses to pain.

After both injections were completed, patients were asked to indicate their preferred injection. This preference was based on their subjective experience and was recorded by selecting the injection number (either the first or second) in the order they were administered for each patient. This method aimed to provide insights into patient comfort and pain perception associated

Inclusion Criteria:

- Individuals classified under American Society of Anesthesiologists classes I and II, indicating a healthy or mild systemic disease status.
- Individuals aged from 18 up to 65 years, encompassing both male and female patients.

- Individuals who required local anesthetic injections bilaterally in the buccal side of the upper posterior teeth. These injections were necessary for various dental procedures, including restorative, endodontic, or prosthodontic treatments, and volunteers as well were to be administered across both sides of upper posterior teeth.
- Individuals must be in good health, not currently taking any medication, and have no contraindications to the use of local anesthesia.
- Individuals who have the ability to understand both oral and written instructions, ensuring effective communication and comprehension throughout the study.

Exclusion Criteria:

- Individuals with allergies to local anesthetics, this is to prevent adverse reactions.

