- Pregnant or nursing women, this is to avoid any potential risks to their health or that of their infants.
- Individuals who were actively taking drugs that could alter pain perception or anxiety levels, such as nonsteroidal anti-inflammatory drugs, opioids, or antidepressants. This was to ensure that the study's findings on pain perception were not influenced by external substances
- Individuals with heavy alcohol consumption. .
- Patients with active pathologies at the injection site, this is to avoid complications and to ensure the accuracy of the study's results.
- Individuals who could not commit to the study's schedule or were unable to give informed consent. This ensured that all participants were fully aware of and agreeable to the study's procedures and requirements.
- Patients who required intravenous sedation for their dental procedures.

Sample Size

The study was designed with a carefully considered sample size to ensure statistical significance and reliability of the results. The sample size for the study was determined utilizing the G-power calculator, resulting in a decision to allocate 40 participants to each of the two groups, with each participant receiving two different injections, thereby evaluating 80 sites in total. This approach allowed for a comprehensive comparison between the two injection types, as each patient served as their control.

Study Design

The study commenced with an initial assessment to determine patient eligibility. Once eligibility was confirmed, the patient was scheduled for their first injection, during which their baseline heart rate was measured before any procedures. Following this, the patient received the first local anaesthesia injection using one of the two methods being compared in the study. After the injection was administered, the patient's heart rate was measured again to record any changes that may have occurred due to the injection then the patient will be asked to evaluate pain intensity with Visual Analogue Scale.

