The patient then returned after one hour, and the patient's heart rate being recorded before the administration of local anaesthesia. For this second injection, the alternative injection method was used on the other side, ensuring that each patient experienced both types of injections. Following the second injection, the patient's heart rate was measured once more to capture the immediate physiological response and the patient will be asked again to evaluate pain intensity with Visual Analogue Scale.

[figure not shown]

Figure 1: Flow chart of the study

This study design is a split mouth clinical trial which allowed for a within-subjects comparison, where each patient's reaction to both injection methods could be directly compared. The heart rate measurements before and after each injection provided objective data on the physiological response to the injections.

Steps of the Experiment

The experimental protocol was meticulously structured to evaluate the efficacy and patient response to two different local anaesthetic delivery systems. The steps were as follows:

Step I: Before administering a local anaesthetic, the patient's heart rate was checked with a pulse oximeter (Beurer Finger Pulse Oximeter). The results were recorded.

Step II: Patients were randomly assigned to get the injection of local anaesthetic at their initial appointment either with the Dentapen system (ramp-up) or with Vibraject. To simplify the protocol, a 27-gauge needle was used for all dental injections with bevel side directly headed to the injected site.

Step III: In the next appointment, after one hour on a digital timer, the other technique was used for the same patients on the other side. Hence, each patient was given local anaesthesia twice, once with the Dentapen system (ramp-up mode) and once with Vibraject.

Step IV: Immediately after each local anaesthesia injection operation, the patient was asked to use the Visual Analogue Scale to score the intensity of reported pain.

Step V: After administering a local anaesthetic, the patient's heart rate was measured with a pulse oximeter (Beurer Finger Pulse Oximeter). The results were recorded.

Step VI: After both injections were administered to each patient, they were asked which injection they would prefer by selecting the injection number (first or second) according to their order for each patient.

Risk of Bias

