To mitigate the risk of bias in this study, several blinding strategies were employed. All patients were blinded to the sequence in which the two anaesthetic techniques were administered. To further reduce variability and potential bias, all procedures were conducted by the same operator and he was trained to ensure all injections to go with same protocol and procedures. This approach eliminated any differences that could arise from operator technique, thus ensuring consistency across all injections. The individual responsible for performing the data analysis was also blinded to which technique was used for each patient. The blinding of the analyst was achieved by using coded data that concealed the identities and the specific techniques used for each patient, thereby maintaining the objectivity of the data interpretation.

Additionally, patients were asked to wear an eye mask during the injection process. The use of masks prevented patients from seeing the syringe and the method of injection being used, which could potentially influence their perception and subsequent reporting of pain. This step was crucial to maintain the integrity of the study's double-blind design, where neither the patients nor the individuals analyzing the data were aware of which technique was being used at any given point, thus preserving the study's methodological rigour.

Injection with the Dentapen® System (Ramp-up Mode)

According to the manufacturer's protocol, the Dentapen electronic syringe was used to administer local anaesthesia. To administer local anaesthesia, a cotton-tipped applicator with 20% benzocaine gel (Topox; Sultan Healthcare, Inc., York, PA) was applied topically after drying the mucosa and placed for 60 seconds using a digital timer. After 60 seconds, the target site was wiped with 2-inch cotton gauze before injecting 0.5 cartridge (0.9 mL) of 3% mepivacaine hydrochloride with no epinephrine (Henry Schein, Melville, NY) which was stored in room temperature. The

needle was advanced into the tissue until it was estimated to be over the root apex while remaining parallel to the tooth's long axis (needle placement). The Dentapen was activated after aspiration to deposit the solution at a medium rate (1 mL/60 s) using the ramp-up mode. Following cartridge deposition, the operator adjusted the participant to an upright seated position so that he or she could independently record his or her perceived pain on the Visual Analogue Scale.

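### Heart rate is read once before and once, at an unstated time, after each injection, so Table 3 shows a pre-to-post change and not the response during the injection

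*Combined protocol and SAP*

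**What the plan says.** The Outcome Measurement section gives the purpose and the schedule together: "heart rate measurements were taken before and after each injection to monitor physiological responses to pain".

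The Study Design section gives the detail.
- At the first injection, "their baseline heart rate was measured before any procedures".
- Then: "After the injection was administered, the patient's heart rate was measured again to record any changes that may have occurred due to the injection". The pain score on the Visual Analogue Scale (VAS) follows.
- At the second injection, heart rate is again recorded beforehand, and then: "Following the second injection, the patient's heart rate was measured once more to capture the immediate physiological response".

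The Steps of the Experiment list the last two actions in the other order: "Step IV: Immediately after each local anaesthesia injection operation, the patient was asked to use the Visual Analogue Scale", followed by "Step V: After administering a local anaesthetic, the patient's heart rate was measured with a pulse oximeter".

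Both injection sections describe "injecting 0.5 cartridge (0.9 mL) of 3% mepivacaine hydrochloride with no epinephrine". They give a Dentapen rate of 1 mL per 60 s and a Vibraject deposition time of about 50 s. Both then have the patient brought upright before the pain score is recorded. The Statistical Analysis section plans a paired t-test of heart rate before against after each injection, and Tables 2 and 3 report those two readings only.

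**The concern.** The stimulus of interest is needle advance, aspiration and deposition. One reading is taken before it starts and one after it has ended, so nothing is recorded while it lasts. The time of the later reading is not given, so it is also unclear how much of any response it could still carry.

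This matters because the heart-rate t-test is one of the two main tests named, and Table 3 contains the only p-value below 0.05 in the report (Dentapen, p = 0.010). A reader could take that figure as evidence that Dentapen provokes a pain response, or take the Vibraject change of 0.275 bpm as evidence of almost none. Readings from outside the stimulus do not measure the size of either response.

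**Working it through.** **1. Reproduce Table 3.** Inputs are the mean and SD of the before-minus-after differences. SE = SD/√n, t = mean/SE, with n − 1 degrees of freedom and a two-sided p.
- Overall (n = 80): SE = 4.18133/√80 = 0.467; t = −0.900/0.467 = −1.925; p = 0.058.
- Dentapen (n = 40): SE = 3.56613/√40 = 0.564; t = −1.525/0.564 = −2.705; p = 0.010.
- Vibraject (n = 40): SE = 4.67940/√40 = 0.740; t = −0.275/0.740 = −0.372; p = 0.712.

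All three rows agree with the table. The rises in SD units are 1.525/3.566 = 0.43 and 0.275/4.679 = 0.06. The arithmetic is sound; the question is what the two readings represent.

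**2. Length of the unobserved interval.** Dentapen deposition is 0.9 mL × 60 s/mL = 54 s. Vibraject deposition is stated as about 50 s. Needle advance and aspiration come on top and are not timed. At the first injection the baseline precedes all procedures, so the 60 s of topical gel also falls between the readings: at least 60 + 50 = 110 s to 60 + 54 = 114 s.

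The Vibraject section ties its 50 s to 0.5 mL with Dentapen. At the stated rate 0.5 mL takes 30 s and 0.9 mL takes 54 s, so those figures need reconciling. The present point does not depend on which is right.

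**3. What the later reading could retain.** The documents give neither the delay nor the rate at which a rise fades, so this is illustration only. If a rise decays exponentially with an assumed half-life h, the share left after t seconds is 0.5^(t/h).

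| Delay after peak | h = 10 s | h = 60 s |
|---|---|---|
| 30 s | 13% | 71% |
| 60 s | 2% | 50% |

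The range runs from almost nothing to most of the rise, so the documents cannot settle how much was lost.

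**4. Position of the later reading.** Study Design puts it before the pain score; Steps IV and V list it after. Because the patient is brought upright before scoring, the order in the step list could also place a change of posture between the injection and the reading.

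**5. Is there a difference between devices?** Table 3 tests each device separately. The difference between the two mean rises is 1.525 − 0.275 = 1.25 bpm. Its SD is √(3.566² + 4.679² − 2r × 3.566 × 4.679), where r is the within-patient correlation of the two changes. That correlation is not reported, so it is assumed over a range (n = 40, 39 df).

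| Assumed r | SD of difference | t | p |
|---|---|---|---|
| −0.2 | 6.43 | 1.23 | 0.23 |
| 0 | 5.88 | 1.34 | 0.19 |
| 0.3 | 4.96 | 1.59 | 0.12 |
| 0.5 | 4.23 | 1.87 | 0.07 |
| 0.7 | 3.35 | 2.36 | 0.02 |

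The difference reaches 0.05 only from about r = 0.58. For the pain scores, the means are 1.550 (Dentapen) and 2.175 (Vibraject), with p = 0.105. Table 4 attributes that p to an unpaired test, so it is not decisive either.

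**The case against.** The plan never claims to measure a peak. It promises readings before and after and delivers them, and an immediate response can reasonably mean one seen straight after the injection. Preferring a reading during deposition is then a choice of endpoint and not the correction of an error. The study is also complete, so the missing values cannot be recovered. Much of this stands. It limits the point to what may be concluded and to a cheap improvement for a repeat. It does not make a pre-to-post change a measure of the response while the injection was painful.

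Two stronger readings are tempting, and the documents support neither.
- A reader might infer that the peak was missed and that the later reading shows recovery, or relief that the injection is over. Nothing in the documents says when heart rate peaks, how fast it falls or how soon it was read. A residual rise may well be present, and Dentapen did show a mean rise.
- A reader might infer that the timing of the reading explains why Dentapen has the lower mean pain score and the larger heart-rate rise. Both devices follow the same schedule, and the Vibraject time was set to match Dentapen. A gap common to both devices lowers sensitivity in both and does not account for opposite directions. Chance has not been excluded for either difference.

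The obvious remedy, the highest value during injection minus a single baseline value, has a fault of its own. The maximum of several fluctuating readings tends to exceed a single reading even when nothing has happened. A before-after test on it would therefore tend to show a rise for both devices by construction.

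**Conclusion.** The point holds as a limit on interpretation. No reading covers needle advance or the 50 to 54 s of deposition, and the later reading is untimed, with two conflicting positions relative to the pain score. Neither p = 0.010 for Dentapen nor 0.275 bpm for Vibraject measures the size of a pain response, and the two rows of Table 3 are not a comparison of devices. The loss of sensitivity cannot be quantified, because there are no data from the interval and the decay figures rest on an assumed half-life. The between-device p-values rest on an assumed correlation. The point leaves the pain scores and the preference result untouched, and it does not show a bias towards either device.

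**What to change.** **Existing report**
- Label Table 3 as pre-to-post-injection change.
- State that nothing was recorded during injection, and give the time of the later reading if it is known.
- Remove wording that presents the Dentapen p-value or the Vibraject change as the size of the pain response or as a difference between devices.
- Reconcile Study Design with Steps IV and V on the order of heart rate and pain score.

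**Any repeat**
- Keep the same oximeter on throughout, assuming it displays continuously (the documents do not describe its display).
- Record heart rate during injection in the same way for both devices, for example at a fixed time in deposition or as a mean over deposition. If a maximum is used, subtract the maximum over a pre-injection window of equal length.
- Make the endpoint the within-patient Dentapen-minus-Vibraject difference in change from the pre-injection value, in place of a before-after test for each device.
- Keep a post-injection reading as secondary, at a fixed time before repositioning and before the pain score.

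The cost is one more value per injection and some motion artefact; a matched maximum also needs a short pre-injection recording window. No additional patients or equipment are needed, on the display assumption above.

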Figure 2: Dentapen used in the study.

Injection with Vibraject

After drying the mucosa, a cotton-tipped applicator with a 20% benzocaine gel (Topox; Sultan Healthcare, Inc., York, PA) was placed for 60 seconds using a digital timer. After 60 seconds, the target site was wiped with another 2-inch by 2-inch cotton gauze and injecting 0.5 cartridge (0.9 mL) of 3% mepivacaine hydrochloride with no epinephrine (Henry Schein, Melville, NY) which was stored in room temperature. The needle was advanced into the tissue until it was estimated to be over the root apex while remaining parallel to the tooth's long axis. The Vibraject was activated after aspiration to deposit the solution slowly at approximately 50 seconds (time necessary to infiltrate 0.5 mL of anesthetic with the dentapen system) for both groups. The time factor was therefore limited to prevent a possible confounding effect in the patients' pain perception. Following cartridge deposition, the operator adjusted the participant to an upright

seated position so that he or she could independently record his or her perceived pain on the Visual Analogue Scale. The Vibraject was selected as the vibrator due to its simple design, battery operation, and ability to be easily attached to a syringe with minimal adjustment to conventional injection procedures. Also, compared to other vibration gadgets, it is reasonably affordable.

Figure 3: Vibraject used in the study.

Visual Analogue Scale scale

The Visual Analogue Scale score was stratified into distinct categories: "0" denoted absence of pain, scores ranging from "1-3" indicated mild pain, "4-6" signified moderate pain, "7-9" represented severe pain, and the maximum score of "10" was designated as indicative of the utmost intensity of pain conceivable.

Statistical Analysis

The statistical analysis for this study was conducted using SPSS Version 20 (IBM-SPSS Inc., Chicago, IL), a robust statistical software package that allows for detailed data management and analysis. The primary statistical tests employed were the paired T-test for analysing the heart rate data and the Wilcoxon test for the Visual Analogue Scale pain scores.

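### Do the stated volume, rate and time of injection undermine the claim that injection time was kept the same for both devices?

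*Combined protocol and SAP*

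**What the plan says.** The combined protocol and SAP describes the two injections in separate sections.

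- **Injection with the Dentapen System (Ramp-up Mode).** The volume is given in the words "before injecting 0.5 cartridge (0.9 mL) of 3% mepivacaine hydrochloride with no epinephrine". The device was then "activated after aspiration to deposit the solution at a medium rate (1 mL/60 s) using the ramp-up mode".
- **Injection with Vibraject.** The volume is given in the same terms: "injecting 0.5 cartridge (0.9 mL) of 3% mepivacaine hydrochloride with no epinephrine". The injection time is set at "approximately 50 seconds (time necessary to infiltrate 0.5 mL of anesthetic with the dentapen system) for both groups". The next sentence draws the design conclusion: "The time factor was therefore limited to prevent a possible confounding effect" in pain perception.

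Neither section reports a measured injection time. A digital timer is mentioned for the topical gel and, under Steps of the Experiment, for the one-hour interval, but not for depositing the solution.

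**The concern.** The words in brackets are the only reason the document gives for choosing about 50 s, and they do not fit the other figures. They name a volume different from the one stated earlier in the same paragraph. Taken with the 50 s, they also imply a Dentapen rate different from the one in the Dentapen section.

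The document itself treats injection time as something that could affect reported pain. If Vibraject injections were in fact given faster than Dentapen injections, the within-patient comparison of Visual Analogue Scale scores would mix the effect of the device with that of delivery rate. Read literally, the bracketed figure allows large imbalances: Dentapen could have taken 90 s for the same volume, or one device could have delivered 44% less solution. Vibraject also has the higher mean pain score in Table 4, which makes the possibility harder to dismiss at first sight.

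**Working it through.** **Inputs**

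| Quantity | Value | Section |
|---|---|---|
| Volume, Dentapen | 0.9 mL | Injection with the Dentapen System |
| Volume, Vibraject | 0.9 mL | Injection with Vibraject |
| Dentapen rate | 1 mL per 60 s | Injection with the Dentapen System |
| Common time | about 50 s | Injection with Vibraject |
| Volume used to explain that time | 0.5 mL | Injection with Vibraject |

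The formula throughout is time = volume ÷ rate. It assumes that 1 mL per 60 s is the average rate over the whole injection.

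**Step 1: the document's own figure, as explained in the brackets.** 0.5 mL ÷ (1 mL/60 s) = 30 s. The stated figure is about 50 s. The gap is 20 s, so the explanation does not reproduce the figure.

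**Step 2: the same calculation with the volume stated for both devices.** 0.9 mL ÷ (1 mL/60 s) = 54 s. The gap from 50 s is 4 s, and 4 ÷ 54 = 7%. This fits a time given as approximate.

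**Step 3: working back from 50 s.**
- At 1 mL per 60 s, 50 s delivers 50 ÷ 60 = 0.83 mL, which is much nearer 0.9 mL than 0.5 mL.
- Delivering 0.9 mL in exactly 50 s needs 0.9 ÷ 50 × 60 = 1.08 mL per 60 s, 8% above the Dentapen rate.

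**Step 4: what the large imbalances require.**
- If 0.5 mL really took 50 s, the rate would be 0.5 ÷ 50 × 60 = 0.6 mL per 60 s, and 0.9 mL would take 0.9 ÷ 0.6 × 60 = 90 s. Against 50 s for Vibraject, that makes Vibraject 90 ÷ 50 = 1.8 times as fast. This reading sets aside the explicit rate in the Dentapen section and the statement that the time applied to both groups.
- If one device delivered 0.5 mL, the volumes would differ by (0.9 − 0.5) ÷ 0.9 = 44%. This reading sets aside the explicit volume in that device's own section.

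**Step 5: which figures disagree.** Three of the four (0.9 mL, 1 mL per 60 s, about 50 s) agree to within 4 s. The fourth, 0.5 mL, appears once, in an explanatory aside. Both sections also use the figure 0.5 as a fraction of a cartridge, so a slip of unit is a plausible origin.

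**Step 6: reach into the analysis.** Under Statistical Analysis, pain is compared by a Wilcoxon test on the scores and heart rate by paired t-tests. Injection time, volume and rate enter neither. The pain difference in Table 4 is 2.175 − 1.550 = 0.625 points with p = 0.105, reported as not significant. Correcting the aside would alter none of these numbers.

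**The case for a change.** The strongest case for acting is that the design claim rests on the faulty aside and nothing else in the document supports it independently. Vibraject is a vibrator attached to a syringe, with no controlled rate stated, so its 50 s was only a target. The Risk of Bias section describes blinding of the patients and the analyst, not of the single operator. No achieved times are given for either device. The 54 s also depends on reading 1 mL per 60 s as an average. The section does not say whether the rate includes the ramp-up. If it is the rate reached afterwards, 0.9 mL takes longer than 54 s and the gap from 50 s widens by an amount the documents do not give.

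Much of this stands. The conflict over 0.5 mL is real, the slip is not confirmed anywhere, and equality of the achieved times cannot be verified. What does not stand is the step from there to an unsupported design claim. The stated volume is the same in both sections, the time is stated as common to both groups, and the operative figures give roughly equal planned times. The document also says only that the time factor was limited, which is weaker than saying it was eliminated. The absence of recorded times limits what can be checked; the arithmetic does not show that the times differed. Nothing in the documents links a gap of a few seconds to the pain scores.

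**Conclusion.** No change to the plan follows. The inconsistency amounts to one figure in an explanatory aside: 0.5 mL at the stated rate takes 30 s, not about 50 s. The volume, rate and time otherwise stated agree to within 4 s, or 7%. The larger figures of 90 s and 44% arise only if the aside overrides explicit statements elsewhere.

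The two device sections should be reconciled as a matter of accurate wording. Which volume, rate or duration is right is for the sponsor to establish from its records, and this review takes no view on it. The reconciliation is clerical: the injections have been given and the results reported, and injection time is not an input to any test.

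The conclusion rests on two assumptions: that 1 mL per 60 s is an average rate, and that injections followed the stated volume and common time. Without reported injection times the second cannot be confirmed, so the text supports an intended common duration but cannot show that it was achieved.
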